1.2 Sample Size

A total sample size of 50 evaluable subjects is planned. An allowance of 10% to account for possible attrition is planned such that up to 55 subjects may be recruited into the study and implanted. The planned sample size of 50 subjects will provide adequate power for the primary efficacy endpoint based on a range of assumptions. Power for this test under a variety of assumptions is provided below. Calculations are based on a one-sample t-test at a two-sided 0.05 alpha level.

Table 1. Power for Sample Size of 50 Evaluable Subjects

True Population CNC Word Score Mean Change	True Population CNC Word Score Standard Deviation for Change		
	30%	40%	50%
20%	>99%	93%	79%
25%	>99%	99%	93%

1.3 Safety

1.3.1 Primary Safety Objective

The purpose of this objective is to describe the safety of cochlear implantation with the CI422 implant in newly implanted adults with expanded indications for candidacy. Safety for this objective will be defined as follows: medical/surgical and device related adverse events will be no worse than with the current approved labeling with regard to type, frequency and seriousness. To address this endpoint, the number and percent of

patients with a device or procedure related adverse event through 6 months postactivation will be reported and tabulated for comparison to current approved labeling (CI422 Physicians Package Insert). Adverse events will be summarized by event type, frequency, seriousness, and whether they are medical/surgical and/or device related. Additionally, any subject at 6 months who experiences a >15 dB shift from their preoperative low frequency (125-1,000 Hz) pure tone average resulting in a low frequency pure tone average of greater than 90dB HL will be reported as an adverse event under this protocol.

1.3.1.1 Analysis of Primary Safety Objective

The number of events, and number and percentage of subjects with each event will be tabulated for adverse events overall and by type. Events will be characterized by severity, seriousness and relatedness. Binomial exact, two-sided, 95% confidence limits will be calculated for device and procedure related adverse event rates.

1.3.2 Secondary Safety Objective

The purpose of the ~~secondary~~ safety objective is to describe resulting hearing levels for each subject at the 6 month endpoint of the study. It is anticipated that no more than 50% of study subjects will present at 6 months with a >15 dB shift from their preoperative low frequency (125-1,000 Hz) pure tone average, resulting in a low frequency pure tone average of greater than 90dB HL. For those subjects who experience the described shift in hearing, it is anticipated that most (>75%) of those subjects will experience an increase in CNC score at 6 months of at least 20% over their preoperative CNC score in the best unilateral condition (treated ear). The CNC Word score in best unilateral condition preoperatively and at 6 months will be compared on a paired per-patient basis, and the number and percentage of subjects for whom the 6 month score is at least 20% better than the preoperative score will be reported. There is no planned formal statistical hypothesis test for this endpoint.

1.4 Efficacy

Efficacy of the Cochlear Nucleus CI422 cochlear implant system will be determined by a comparison of preoperative vs. postoperative outcomes measures. The speech measures for this purpose are the CNC Word Test and the AzBio sentences in noise. The primary and secondary efficacy endpoints will be based on analyses of designated test measures at the 6-month postactivation interval.

1.4.1 Primary Efficacy Objective

The Primary Efficacy Objective for this study is to understand if cochlear implantation with a Cochlear Nucleus CI422 cochlear implant in adult patients with expanded indications results in improved speech understanding at 6 months postactivation, as measured by performance on an open-set word recognition test, in the best unilateral listening condition of the implanted ear.

- On the CNC word measure, the group mean score for best unilateral listening condition at 6 months will be better than the group mean score in the preoperative, unilateral aided condition.

The primary hypothesis to be tested in this analysis is the following: that the 6 month postoperative performance is significantly different from preoperative performance in the treated ear. The null and alternative hypotheses are given below.

$$H_{01}: \bar{I}_{Post} - \bar{I}_{Pre} \leq 0 \text{ versus } H_{a1}: \bar{I}_{Post} - \bar{I}_{Pre} > 0$$

Where \bar{I}_{Pre} is the CNC word score in quiet obtained with a hearing aid preoperatively in the ear to be implanted, and \bar{I}_{Post} is the CNC word score in quiet obtained at 6 months post sound processor activation in the treated ear. The test will be based on a one-sample t-test of the paired difference in pre and post results and performed at the one-sided 0.025 alpha level.

1.4.2 Secondary Efficacy Objectives

Secondary efficacy objectives will be determined by further comparison of group means for preoperative vs. 6 months postoperative outcome measures in best unilateral and best bilateral listening conditions. The speech measures for this purpose are the CNC Word Test and the AzBio sentences in noise.

Secondary efficacy endpoints are as follows:

- On the CNC word measure, the group mean score for best bilateral listening condition at 6 months will be better than the group mean score in the preoperative, bilateral aided condition.
- On the AzBio sentences-in-noise measure, the group mean score for best bilateral listening condition at 6 months will be better than the group mean score in the preoperative, bilateral aided condition.
- On the AzBio sentences-in-noise measure, the group mean score for best unilateral listening condition at 6 months will be better than the group mean score in the preoperative, unilateral aided condition.

The hypothesis test for each of the secondary efficacy endpoints is as follows:

$$H_{01}: \bar{I}_{Post} - \bar{I}_{Pre} \leq 0 \text{ versus } H_{a1}: \bar{I}_{Post} - \bar{I}_{Pre} > 0$$

Where \bar{I}_{Post} is the post-implant value and \bar{I}_{Pre} is the pre-implant value. Each test will be based on a one sample paired t-test of the difference in pre and post results. All tests will be performed at the one-sided 0.025 alpha level.

1.4.3 Type I Error Control

The secondary efficacy objectives will be tested only if the primary efficacy objective is successful. Each secondary objective will be tested sequentially with the subsequent test performed only if the first is successful. Therefore, the overall Type I error of 5% is

preserved and no increase in sample size to protect against multiplicity is required. The sequential order of the testing procedure is as follows:

1. Bilateral 6 month CNC Word measure
2. Bilateral 6 month AzBio sentences-in-noise measure
3. Unilateral 6 month AzBio sentences-in-noise measure

1.5 Additional Statistical Analyses

1.5.1 Analysis of Baseline Characteristics

The baseline characteristics of the study groups will be presented descriptively. Quantitative variables such as age will be presented with mean, standard deviation, median, minimum and maximum. Qualitative variables such as gender will be presented with number with the condition, the sample size, the percentage, and the 95% two-sided exact binomial confidence intervals.

1.5.2 Supportive Efficacy Analyses

Supportive efficacy analyses will include analysis of individual data for all measures. Individual scores obtained at 6 months will be compared with those obtained, on the same measures preoperatively, based on the binomial model where appropriate (see Thornton and Raffin, 1978) to establish the proportions of those subjects showing improvement, no change, and decrement in performance including:

- On the CNC word measure, most (> 75%) of the subjects at 6 months will score equal to or better in their best unilateral listening condition than they did in the preoperative unilateral aided condition.
- On the AzBio sentences-in-noise measure, most (> 75%) of the subjects at 6 months will score equal to or better in their best unilateral listening condition than they did in the preoperative, unilateral aided condition.
- On the CNC word measure, most (> 75%) of the subjects at 6 months will score equal to or better in their best bilateral listening condition than they did in the preoperative, bilateral aided condition.
- On the AzBio sentences-in-noise measure, most (> 75%) of the subjects at 6 months will score equal to or better in their best bilateral listening condition than they did in the preoperative, bilateral aided condition.

Regression analyses of efficacy parameters will also be done, adjusted for baseline covariates of interest including:

- Age at implantation
- Duration of hearing loss
- Gender

Longitudinal analyses (to 12 months) of efficacy parameters will be analyzed. In addition, change in low-frequency hearing sensitivity (125 to 1000 Hz) for each subject will be documented and ultimately reported as the total number and percentage of subjects who fall within the ranges given in the following table. The impact of any such changes will be assessed in light of overall speech perception outcomes.

Change in low-frequency hearing sensitivity
≤10 dB
>10 dB and ≤20 dB
>20 dB and ≤30 dB
>30 dB

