#### **4.1.1 Inclusion Criteria**

1. Eighteen years of age or older at the time of implantation
2. Moderate low frequency thresholds up to and including 1000 Hz, severe to profound high frequency (above 3000 Hz) sensorineural hearing loss.
3. Minimum of 30 days experience with appropriately fit bilateral amplification, fit using the standardized NAL fitting method described in the *Fitting and Use of Hearing Aids* section below
4. Aided CNC word recognition score (mean of two lists) between 10% and 50%, inclusive (i.e.,  $10\% \leq \text{score} \leq 50\%$ ), in the ear to be implanted
5. Aided CNC word recognition score (mean of two lists) in the contralateral ear equal to, or better than, the ear to be implanted but not more than 70%
6. Willingness to use bimodal stimulation (i.e., a cochlear implant on one ear and a hearing aid on the contralateral ear) through at least 6-months postactivation
7. English spoken as a primary language

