#### **5.4.1.3 Candidacy Assessment**

- Air conduction thresholds at 125, 250, 500, 750, 1000, 1500, 2000, 3000, 4000, 6000, 8000 Hz;
  - Unilateral each ear
- Bone conduction thresholds at 125, 250, 500, 750, 1000, 1500, 2000, 4000 Hz;
  - Unilateral each ear

Note: Clinician will need to confirm the subject's response to any pure tone stimulus presented at 125 and 250 Hz as auditory "heard" versus vibrotactile "felt" and record the response accordingly.

- Aided thresholds at 125, 250, 500, 750, 1000, 1500, 2000, 3000, 4000^7 Hz;
  - Unilateral each ear with contralateral ear plugged
- Tympanometry in each ear
- CNC Word Test – Two lists at 60 dB(A) in each of the following conditions:
  - Unilateral aided each ear with contralateral ear plugged

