##### **5.4.2.1 Speech Perception Testing**

- CNC Word Test – Two lists at 60 dB(A)
  - Bilateral Aided
- AzBio Sentences in Noise – One list at 65dB(A) with a +5 dB SNR in each of the following conditions
  - Unilateral Aided, ear to be implanted with contralateral ear plugged
  - Bilateral Aided
- AzBio Sentences in Noise – One list at 65dB(A) with a +10 dB SNR in each of the following conditions
  - Unilateral Aided, ear to be implanted with contralateral ear plugged
  - Bilateral Aided

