1.6 Justification of Pooling Across Study Sites

Pooling data from study sites will be done based on the following: all sites will have the same protocol, the sponsor will monitor the sites to assure protocol compliance, and the data gathering mechanism (case report forms and data acquisition) will be the same across all study sites (Meinert, 1986). Maximum enrollment at individual sites will be set at 10 subjects, in an attempt to improve generalizability of the results.

Consistency of the primary efficacy endpoints between sites will be assessed by testing for a difference between sites in the change in CNC word score from preoperative to 6 months postoperative via an analysis of variance model, with the change in CNC word score as the outcome and site as the factor. A p-value for the site factor of less than 0.10 will be considered evidence of differences between sites for the primary efficacy outcome. If there is evidence of a difference, additional analyses will be performed to explore the possible role of baseline characteristics to explain the results. Results for the primary efficacy endpoint will also be presented separately by site, irrespective of the test of differences between sites to help understand both qualitative and non-significant differences between sites.

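### The supportive regressions do not prespecify the preoperative score as a covariate or state their outcome, and the site ANOVA uses site alone, so covariate and site effects may partly reflect baseline case mix

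*SAP*

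**What the plan says.** **Supportive regressions (SAP 1.5.2).** "Regression analyses of efficacy parameters will also be done, adjusted for baseline covariates of interest including" introduces three items: age at implantation, duration of hearing loss and gender. The preoperative score is not among them. The section does not say whether the regression outcome is the 6-month score or the change from before surgery.

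**Site comparison (SAP 1.6, same text in protocol 8.3).** The ANOVA is specified "with the change in CNC word score as the outcome and site as the factor". The rule is "A p-value for the site factor of less than 0.10 will be considered evidence of differences between sites". If it is met, "additional analyses will be performed to explore the possible role of baseline characteristics to explain the results"; which characteristics is not stated. Results by site are presented whatever the test shows.

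**Scores available.** Implant-ear CNC is measured at candidacy (protocol 5.4.1.3: "Unilateral aided each ear with contralateral ear plugged"). Bilateral CNC, and AzBio in both listening conditions at +5 and +10 dB SNR, are measured at the baseline evaluation (protocol 5.4.2.1). Entry restricts the implant-ear score: "Aided CNC word recognition score (mean of two lists) between 10% and 50%, inclusive" (protocol 4.1.1).

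**The concern.** Subtracting the preoperative score does not adjust for it. A change score fixes the slope of the 6-month score on the preoperative score at 1. Two features make a lower slope plausible here:

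- CNC is bounded at 0 and 100%, so a subject who starts at 10% has more room to gain than one who starts at 50%.
- The preoperative score carries test error and is also the score on which subjects are selected. Two 50-word lists at a true score of 30% have a binomial SD of sqrt(0.3 × 0.7 / 100) = 4.6 points.

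If the slope is below 1, any site or covariate associated with starting score absorbs part of that relation when change is the outcome. If the outcome is the 6-month score, the same happens whenever the slope is not 0. Because SAP 1.5.2 does not state the outcome, a reader cannot tell which case applies. An apparent effect of age or duration, or a site flag at 0.10, could then be baseline case mix. A real site difference could equally be hidden.

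**Working it through.** **1. The plan's own figure.** SAP 1.2 gives power for 50 evaluable subjects, one-sample t-test, two-sided 0.05. Exact noncentral-t power with noncentrality (mean change / SD) × sqrt(50):

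| Mean change | SD 30 | SD 40 | SD 50 |
|---|---|---|---|
| 20 | 99.6% | 93.4% | 79.2% |
| 25 | 99.99% | 99.1% | 93.4% |

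All six cells agree with the SAP table. That test involves no covariates, so nothing below alters it.

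**2. Inputs for the covariate question**

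- From the plan: n = 50; SD of change 30, 40 or 50; preoperative implant-ear CNC between 10 and 50.
- Assumed: preoperative SD s0 = 40 / sqrt(12) ≈ 11.5 (uniform over the entry range). It cannot exceed about 20, half the range.
- Assumed: slope b of the 6-month score on the preoperative score, from 0 to 1.

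**3. Precision.** Var(change) = (b − 1)² × s0² + Ve, where Ve is the residual variance given the preoperative score. Adjustment takes the residual SD from SD(change) to sqrt(Ve). For SD 30 and b = 0: Ve = 900 − 132.25 = 767.75, sqrt(Ve) = 27.7, and 1 − 27.7/30 = 7.6%. Reduction in SE for a change outcome, s0 = 11.5:

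| SD of change | b = 0 | b = 0.5 | b = 1 |
|---|---|---|---|
| 30 | 7.6% | 1.9% | 0% |
| 40 | 4.2% | 1.0% | 0% |
| 50 | 2.7% | 0.7% | 0% |

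At the extreme s0 = 20, the SD 30 row becomes 25.5%, 5.7% and 0%. If the outcome is the 6-month score, with SD of change 30 and s0 = 11.5, the reductions are 0%, 1.9% and 6.6%.

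**4. Bias from omission.** For a baseline difference D between sites or covariate levels, the unadjusted effect shifts by (b − 1) × D for a change outcome and by b × D for a 6-month outcome. With D = 10 points:

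| Outcome | b = 0 | b = 0.5 | b = 1 |
|---|---|---|---|
| Change | −10 | −5 | 0 |
| 6-month score | 0 | +5 | +10 |

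Illustration for duration: with b = 0.5 and an assumed correlation of −0.3 between duration and preoperative score, the shift in a change model is −0.5 × −0.3 × 11.5 = 1.7 points per SD of duration. The SE of such an effect with 50 subjects is about 30/sqrt(50) = 4.2 to 50/sqrt(50) = 7.1 points, so the shift is about 0.24 to 0.4 of an SE.

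With the preoperative score in the model, the coefficients of the other covariates are identical for either outcome, so naming it also settles most of the ambiguity about the outcome.

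**5. Site test at 0.10.** Simulation with n = 50, SD of change 30, s0 = 11.5, preoperative scores clipped to 10-50, no true site effect given the preoperative score, and 4,000 replicates per scenario. Proportion flagged by the planned ANOVA:

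| Preoperative site means | b | 10 sites | 20 sites |
|---|---|---|---|
| Differ with SD 8 | 0 | 24% | 18% |
| Differ with SD 8 | 0.5 | 13% | 11% |
| Differ with SD 8 | 1 | 9% | 9% |
| No systematic difference | 0, 0.5 or 1 | about 10% | about 10% |

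The adjusted test stayed at about 9-10% throughout. A between-site SD of 8 is a strong assumption: 64/132 is nearly half of the preoperative variance.

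**The case against.** The case for leaving the text alone has real substance.

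- **The list is open.** The word introducing the three covariates does not exclude the preoperative score. This stands: a reader might infer that the plan leaves the score out, but the documents show only that it is not prespecified. An open list still lets an obvious covariate be added or dropped after the results are seen.
- **SAP 1.6 already looks at baseline characteristics and always shows results by site.** This also stands. A flag caused by case mix would lead to that exploration, and no rule says that p below 0.10 blocks pooling. But the step is conditional, names no characteristic, and is not reached when baseline mix hides a difference.
- **The ANOVA checks consistency of the primary endpoint, which is unadjusted change.** This is a fair reason to keep the planned model, and to put the adjusted one beside it.
- **Adjustment changes the question for duration.** Longer hearing loss may itself lower the preoperative score, so conditioning on that score removes part of the association. The score is also range-restricted and measured with error, so adjustment does not guarantee unconfounded effects. Both points stand and shape the fix.
- **No decision changes.** These analyses are supportive. This stands and limits the importance.

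A reader might also expect a large gain in precision. A correlation of 0.3 to 0.5 between change and baseline would cut the residual SD by 5-13%. With s0 = 11.5 and slopes of 0 to 1, however, the correlation cannot exceed 11.5/30 = 0.38 at the plan's smallest SD of change. A slope of 0.5 gives 5.75/30 = 0.19 down to 5.75/50 = 0.12, a gain of about 1-2%.

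**Conclusion.** The gap is real but minor. The preoperative score is not prespecified in the supportive regressions, their outcome is not stated, and the site model has site as its only term, although the scores are in hand.

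It would be tempting to conclude that the covariate and site effects will be confounded and imprecise. The documents do not support that. Confounding needs both a baseline imbalance and a slope other than 1 (change outcome) or other than 0 (6-month outcome), and the plan gives neither quantity. Under the stated assumptions the precision gain for implant-ear CNC change is about 0-8% in SE. That range does not carry over to AzBio or bilateral CNC, which have no 10-50% entry range.

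The stronger reason to act is confounding: in the assumed 10-site scenarios the planned test flagged 24% or 13% where 10% is nominal. There was no inflation when site means did not differ systematically or the slope was 1. The primary test, its power and the secondary hierarchy are unaffected.

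**What to change.** - **SAP 1.5.2:** state the 6-month score as the regression outcome and name the preoperative score on the same measure and listening condition (for AzBio, the same SNR) as a covariate. Also report the duration effect without the preoperative score, since duration may act through it.
- **SAP 1.6 and protocol 8.3:** add the preoperative unilateral aided CNC score of the implanted ear to the site model, or report that adjusted model beside the planned ANOVA whatever its p-value.

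The cost is one sentence per section and one error degree of freedom (for example, 40 to 39 with 10 sites and 50 subjects). No new data are needed.

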1.6 Justification of Pooling Across Study Sites

Pooling data from study sites will be done based on the following: all sites will have the same protocol, the sponsor will monitor the sites to assure protocol compliance, and the data gathering mechanism (case report forms and data acquisition) will be the same across all study sites (Meinert, 1986). Maximum enrollment at individual sites will be set at 10 subjects, in an attempt to improve generalizability of the results.

Consistency of the primary efficacy endpoints between sites will be assessed by testing for a difference between sites in the change in CNC word score from preoperative to 6 months postoperative via an analysis of variance model, with the change in CNC word score as the outcome and site as the factor. A p-value for the site factor of less than 0.10 will be considered evidence of differences between sites for the primary efficacy outcome. If there is evidence of a difference, additional analyses will be performed to explore the possible role of baseline characteristics to explain the results. Results for the primary efficacy endpoint will also be presented separately by site, irrespective of the test of differences between sites to help understand both qualitative and non-significant differences between sites.

1.7 Missing Data

All efforts will be put forth to ensure near complete follow-up, with particular focus on the assessment of the primary outcome and occurrence of adverse events. Regular reminders of subject follow-up due dates will be provided to participating centers to facilitate scheduling of follow-up visits.

In the event a subject is withdrawn prior to the 6-month assessment, the primary analysis of the primary efficacy endpoint will involve imputing the pre-operative CNC word test score for the 6 month CNC word test. This is equivalent to treating each subject with a missing 6 month result as unchanged from baseline. The p-value for the primary efficacy statistical hypothesis test will be calculated using this imputation to understand the impact of missing data on the primary result.

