### 8.4 Missing Data

All efforts will be put forth to ensure near complete follow-up, with particular focus on the assessment of the primary outcome and occurrence of adverse events. Regular reminders of subject follow-up due dates will be provided to participating centers to facilitate scheduling of follow-up visits.

Cochlear

In the event a subject is withdrawn prior to the 6-month assessment, the primary analysis of the primary efficacy endpoint will involve imputing the pre-operative CNC word test score for the 6 month CNC word test. This is equivalent to treating each subject with a missing 6 month result as unchanged from baseline. The p-value for the primary efficacy statistical hypothesis test will be calculated using this imputation to understand the impact of missing data on the primary result.

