1.0 Data Analyses

1.1 Study Population

Any subject in whom the Cochlear Nucleus CI422 cochlear implant is attempted to be implanted under this protocol will comprise the intention-to-treat population (ITT). The primary efficacy and safety endpoints will be evaluated with the ITT population. A tipping point sensitivity analysis will be conducted by the methods described in the missing data section to address any missing data.

The effectiveness analyses will also be done on the completed cases (CC) population; treated subjects who had follow-up of the primary endpoint at the protocol prescribed time. A supportive analysis of the primary endpoint will be done in the CC population. Additional analyses will be examined only in the CC population.

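### The zero-change p-value cannot show the impact of missing data: near the 0.025 threshold it practically equals the complete-case p-value

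*SAP*

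**What the plan says.** SAP 1.4.1 tests the paired change in CNC score against zero with a one-sample t-test, "performed at the one-sided 0.025 alpha level". SAP 1.1 makes ITT (implantation attempted) the primary population and adds: "A supportive analysis of the primary endpoint will be done in the CC population".

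For subjects withdrawn before 6 months, SAP 1.7 and Protocol 8.4 carry the preoperative score forward. Protocol 8.4 explains: "This is equivalent to treating each subject with a missing 6 month result as unchanged from baseline". Both sections then say that the p-value is "calculated using this imputation to understand the impact of missing data on the primary result".

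SAP 1.1 also promises a tipping-point sensitivity analysis and refers to the missing-data section for its method. SAP 1.7 contains only the single zero-change imputation. On sample size, SAP 1.2 says "A total sample size of 50 evaluable subjects is planned" and "An allowance of 10% to account for possible attrition is planned such that up to 55 subjects may be recruited into the study and implanted".

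**The concern.** The imputed value is exactly the null value of the test, and it enters as a constant. Each zero pulls the mean towards zero, but it also lowers the standard error by almost the same factor. The ratio of the two, which decides significance, hardly responds to how many subjects were lost.

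The plan nevertheless presents this p-value as its gauge of missing-data impact, with the CC analysis as support. In a single-arm, open-label trial, a report that the ITT and CC p-values agree would naturally be read as robustness to dropout, although the arithmetic nearly guarantees that agreement. What is at stake is what the trial can claim about dropout, rather than the validity of the primary test.

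**Working it through.** **Inputs.** n = 55 implanted, 50 evaluable, so 5 missing (5/55 = 9.1%); mean change 20 or 25 points and SD 30, 40 or 50 (all SAP 1.2). Baseline CNC in the ear to be implanted is 10% to 50% (Protocol 4.1.1, criterion 4). Losses of 15 and 27 of 55 are assumed, to show the range.

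**The plan's own figure.** SAP 1.2 states: "Calculations are based on a one-sample t-test at a two-sided 0.05 alpha level". The noncentral t with 50 subjects gives 99.6%, 93.4% and 79.2% for mean 20, and above 99.9%, 99.1% and 93.4% for mean 25. The power table reproduces.

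**Effect of the zeros on t.** Take k observed changes with mean m and SD s, and j = n − k zeros.

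- Mean = km/n
- Sum of squares = (k−1)s² + (kj/n)m², divided by n − 1 for the variance
- Hence t_imp² = t_cc² × [k(n−1)/n] / [(k−1) + j·t_cc²/n]

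With t_cc = 2.01 and k = 50: 4.0401 × 49.091/49.367 = 4.017, so t_imp = 2.004.

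| Missing | t_imp | One-sided p, CC | One-sided p, zero-filled |
|---|---|---|---|
| 5 | 2.004 | 0.0250 | 0.0250 |
| 15 | 1.989 | 0.0257 | 0.0259 |
| 27 | 1.958 | 0.0273 | 0.0277 |

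**Agreement of verdicts.** In 200,000 simulated trials per scenario (mean 20, SD 30 to 50, dropout unrelated to outcome), the two tests reached different verdicts in at most 0.034% of trials with 5 missing and 0.39% with 27 missing.

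**Estimate and interval.** Take observed mean 20, SD 50, 5 missing.

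- CC: standard error 50/√50 = 7.07; 20 ± 14.2, lower limit 5.8.
- Zero-filled: mean 50 × 20/55 = 18.2; variance (49 × 2500 + 4.545 × 400)/54 = 2302; standard error √(2302/55) = 6.47; 18.2 ± 13.0, lower limit 5.2.
- Half-width ratio: 12.97/14.21 = 0.91, so 9% narrower. With 15 missing: 11.74/15.99 = 0.73, so 27% narrower.

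At t_cc = 2.01 the zero-filled interval is also 4% (5 missing) and 14% (15 missing) narrower than if all 55 had been measured with the same SD.

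**What does move the p-value.** Replace the zeros by a common change d: mean = (km + jd)/n, sum of squares = (k−1)s² + (kj/n)(m − d)². At observed mean 20, SD 50:

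| Missing | p at d = 0 | p at −10 | p at −20 | p at −40 | p at −50 | Crosses 0.025 at about |
|---|---|---|---|---|---|---|
| 5 | 0.0034 | 0.0053 | 0.0082 | 0.019 | 0.028 | −47 |
| 15 | 0.0081 | 0.027 | 0.075 | 0.30 | 0.45 | −9 |

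A fall of 47 points is possible only from a baseline of at least 47%. A fall of 9 points is possible for every eligible subject.

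**The case against.** Several points on the other side stand.

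- A reader might infer that the ITT and CC p-values coincide whatever the dropout and effect. They do not. The term j·t_cc²/n grows with the effect. At mean 25/SD 30 the p-value ratio is 1.41 with 5 missing (1.7e-7 vs 2.4e-7) and 2.30 with 27 missing (7.4e-5 vs 1.7e-4). Both values are then far below 0.025, so the verdict is unaffected.
- A reader might infer that ITT and CC are one analysis. They are not. The estimate shrinks by k/n. The populations also differ: CC requires follow-up at the prescribed time, and Protocol 6.2 sets a ±30-day window, so an out-of-window score could count in ITT but not in CC.
- A reader might infer that the zero-filled test is too liberal. Under no true change and random dropout it rejects at about 2.5%. In the SAP 1.2 scenarios its lower limit lies below the CC limit, as in the worked example.
- The plan names no confidence interval for the primary efficacy endpoint. The interval point is a warning about any that is reported.
- The plan does not rest on this p-value alone, since SAP 1.1 promises a tipping-point analysis. The promise does not cure the problem, because the section it refers to gives no such method. The only missing-data assessment actually specified is the p-value that cannot show an impact.

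**Conclusion.** The point holds in a limited form. Near the decision threshold the zero-change p-value carries practically no information about missing data: it differs from the complete-case value by less than 0.001 even with 27 of 55 missing. Agreement between the two therefore says nothing about robustness. The verdict is almost always shared; the estimate and the interval are not.

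A reader might go further and infer that the primary result is in danger. The documents do not support that at the planned attrition. With 5 missing and an observed mean of 20/SD 50, the weakest cell of the power table, the missing subjects would need to lose about 47 points each, close to or beyond what their baselines allow. The exposure comes with heavier dropout (about −9 points with 15 missing) or an observed result close to the threshold.

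This rests on dropout unrelated to outcome in the simulations, on a common imputed change for all missing subjects in the tipping figures, and on assumed losses beyond 5 of 55.

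**What to change.** In SAP 1.7 and Protocol 8.4:

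1. Keep zero-change imputation as the primary analysis if wished, but delete the statement that its p-value shows the impact of missing data.
2. Report the ITT and CC mean changes side by side with 95% intervals. Do not compute the ITT interval as if the constant zeros had been observed; state how uncertainty in the missing values enters. Plain normal draws centred at zero with the observed SD are a poor choice. At SD 40, about 11% (baseline 50%) to 40% (baseline 10%) of imputed scores would fall below 0% correct, and draws centred at zero do not test an average outcome worse than baseline.
3. Write out the tipping-point analysis promised in SAP 1.1: a grid of imputed changes from zero downwards, stopped for each subject at 0% correct. Report the value at which one-sided p crosses 0.025, or state that it never does.

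The cost is some SAP wording and a little more analysis work. It needs no extra subjects or visits and leaves the primary test unchanged.
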